PROTOCOL

Acceptability, feasibility and impacts of remote symptom monitoring and automated treatment plans in children with Cystic Fibrosis (CF) on highly effective modulators: a pilot randomised controlled trial.

HREC #: 91117

Protocol Version and date:
Version 2 28/10/2022

Document history:

Version Number and Date	Summary of changes
Version 1 26.10.2022	Initial submission
Version 2 28.10.2022	Re-submission 1 to address ethics queries

Statement of Compliance

This clinical trial will be conducted in compliance with all stipulation of this protocol, the conditions of the ethics committee approval, the NHMRC National Statement on ethical Conduct in Human Research (2007 and all updates), the Integrated Addendum to ICH E6 (R1): Guideline for Good Clinical Practice E6 (R2), dated 9 November 2016 annotated with TGA comments and the NHMRC guidance Safety monitoring and reporting in clinical trials involving therapeutic goods (EH59, 2016).

PROTOCOL SYNOPSIS

TITLE	Acceptability, feasibility and impacts of remote symptom monitoring and automated treatment plans in children with Cystic Fibrosis (CF) on highly effective modulators: a pilot randomised controlled trial.
STUDY DESCRIPTION	This is a pilot randomised controlled trial with participants randomly allocated to remote symptom monitoring and automated treatment plan care model (intervention group) versus usual hospital CF care (control group). The two models of care will be compared and the feasibility and acceptability of the new model of care will be assessed.
OBJECTIVES	
Primary:
 
 1. To assess the uptake and feasibility of the remote monitoring and automated treatment plans 2. To assess the impact and acceptability of the remote system monitoring and automated treatment plans on family experience 3. To assess the impact and acceptability of the remote system monitoring and automated treatment plans on CF multidisciplinary team (MDT) experience 
Secondary:
 
 1. To understand changes in outcome measures over time between the two groups in children on highly effective modulators 2. To assess the cost-effectiveness of the remote monitoring and automated treatment plans compared to usual care by undertaking a health economic evaluation from healthcare and societal (family) perspectives.

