OUTCOMES AND OUTCOME MEASURES	
 1. To assess the uptake and feasibility of the remote monitoring and automated treatment plans 
 a. Number of symptom surveys completed (retention of participants and survey completion rate) b. Number of tasks completed c. Number of contacts between CF team and family (staff workload) 2. To assess the impact and acceptability of the remote system monitoring and automated treatment plans on family experience 
 a. Semi structured interviews with participants investigating beliefs, acceptability and feasibility of the remote symptom monitoring and automated treatment plan care model b. Overall service satisfaction 3. To assess the impact and acceptability of the remote system monitoring and automated treatment plans on CF MDT experience 
 a. Semi structured interviews with staff investigating beliefs, acceptability and feasibility of the remote symptom monitoring and automated treatment plan care model 4. To understand changes in outcome measures over time between the two groups in children on highly effective modulators 
 a. Change in child lung function (Forced Expiratory Volume in 1 Second, FEV₁) b. Number of detected pulmonary exacerbations c. Antibiotic usage d. Child Quality of Life (measured with the CF Questionnaire Revised, CFQ-R and EQ-5D-Y)

Study Name: Acceptability, feasibility and impacts of remote symptom monitoring and automated treatment plans in children with Cystic Fibrosis (CF) on highly effective modulators: a pilot randomised controlled trial.

Protocol Number: 91117

Version & date: version 2, 28.10.2022

	
5. To assess the cost-effectiveness of the remote monitoring and automated treatment plans compared to usual care by undertaking a health economic evaluation from healthcare and societal (family) perspectives.
 
 a. Number of detected pulmonary exacerbations b. Antibiotic usage c. Number of hospital admissions and ED presentations d. Hospital length of stay e. Travel time and costs for appointments and admissions f. Caregiver time off work & patient time off school to attend appointments/admissions g. Number of contacts between CF team and family

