Version & date: version 2, 28.10.2022

Recruitment:

Potential participants will be recruited through the following multi-pronged approach:

Patients

- *Self-enrolment:*

Participants will be sent information regarding the study, including study overview and contact details for the study team, in a letter signed by the CF centre director via the RCH Portal (Appendix 1). The letter will include a QR code taking interested families directly to a screening questionnaire for study eligibility (Appendix 2). If meeting eligibility criteria the participant will be linked to the PICF (Appendix 3) where they can read in more detail about the study. There will also be a child information sheet regarding the study. Families will indicate consent by checking a box at the start of the online survey and will subsequently be recruited into the study. Families will then complete the baseline demographic survey (Appendix 4). The initial demographic survey will include an item seeking their permission to contact them to potentially participate in a qualitative interview via MS Teams if allocated to the intervention arm. These families will be invited to include a preferred contact mode (either email or telephone) and a member of the research team will contact parents or carers via their preferred contact mode to invite them to participate in the interview.

- *Phone call enrolment:*

For those who do not self-enrol from the initial letter, a follow up phone call will be made by the principal investigator (an RCH CF physiotherapist) one week after letter has been sent out, to ascertain interest in the study. The principal investigator will explain the study to the potential participant. Interested families will complete the screening survey (Appendix 2) over the phone with the PI and will be sent links to the: 1) PICF (Appendix 3), 2) Online consent, and 3) Baseline demographic survey (Appendix 4) by the RCH portal.

- *Clinic enrolment (face to face or via telehealth):*

Potential participants attending their routine CF clinic may be approached by the principal investigator to ascertain their interest in the study. The principal investigator will explain the study to the potential participant. Interested families will complete the: 1) screening survey (Appendix 2) 2) PICF (Appendix 3), 3) consent, and 4) Baseline demographic survey (Appendix 4) in person or if time does not permit will be sent links by the RCH portal.

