Spirometry will be performed either in person or via telehealth as is usual care for children with CF. Spirometry and lung volumes will be measured in accordance with international standards, utilising Jaeger Masterscreen body or Pneumo respiratory function equipment [32]. All pulmonary function testing will be carried out by experienced paediatric physiologists. If spirometry is performed at RCH, height will be measured to the nearest 0.1cm utilising a stadiometer (Seca) and weight will be measured with minimal clothing the nearest 0.1kg (Tanita). In keeping with current clinical practice, for spirometry performed via telehealth, anthropometric data will either be reported from measurements taken at home or the most recent in hospital measurements will be used.

Interviews:

Semi structured interviews (caregivers)

The initial demographic survey will include an item seeking caregiver permission to contact them to participate in a qualitative interview via MS Teams if in the intervention arm. These families will be invited to include a preferred contact mode and a member of the research team will contact caregivers via their preferred contact mode to invite them to participate in the interview. The PICF (Appendix 3 & 5) will outline that any interviews as a part of the study are purely voluntary.

Semi-structured interviews will be scheduled based on feasibility and preference. At the initial time of consent, the researcher will describe to the participants the reason for conducting the interview by providing a copy of the PICF (Appendix 3 & 5). The researcher will invite and respond to any questions or concerns from participants and invite participants to sign a consent form.

Participants will be informed of confidentiality procedures and that the interview will be audio recorded on MS Teams for research purposes. The participant will be advised that they can turn off their camera if they do not wish for a visual image to be recorded. If participants decline to be recorded, the interview will proceed with the PI taking notes of discussion. Prior to commencing the interview, the researcher will inform participants that they are able to stop the interview at any time

and revoke their consent to participate during or after the interview. In this event, interview recordings and transcripts will be removed from the study and destroyed. The withdrawal of participants at any part of the study will not affect their care in any way.

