We aim to conduct interviews with up to 15 parents. The interviews aim to understand caregiver's experiences of the new model of care, including potential benefits, risks, ease of use and future improvements. Interview guide for parent semi structured interviews can be found in Appendix 14.

Semi structured interviews (CF MDT)

Members of the CF MDT will be approached by the principal investigator via email to ascertain their interest in participating in a semi-structured interview. Interviews will be scheduled based on feasibility and preference.

At the initial time of consent, the researcher will describe to the participants the reason for conducting the interview by providing a copy of the PICF (Appendix 6). The researcher will invite and respond to any questions or concerns from participants and invite participants to sign a consent form.

Participants will be informed of confidentiality procedures and that the interview will be audio recorded on MS Teams for research purposes. The participant will be advised that they can turn off their camera if they do not wish for a visual image to be recorded. If participants decline to be recorded, the interview will not proceed. Prior to commencing the interview, the researcher will inform participants that they are able to stop the interview at any time and revoke their consent to participate during or after the interview. In this event interview recordings and transcripts will be removed from the study and destroyed.

We will aim to perform interviews with as many members of the CF MDT as possible, aiming a minimum of 5 staff members. The interview guide for CF MDT semi-structured interviews can be found in Appendix 15 and aims to explore experiences of the new model of care, including potential benefits, risks, ease of use and future improvements.

EPIC reports

Pre-made reports have been created in EPIC associated with the remote symptom monitoring and automated treatment plan model of care. The report collates the following information for intervention group participants only:

- Number of baseline surveys completed
- Number of symptom surveys completed
- Number of exacerbations
- Length of exacerbation
- Symptoms experienced with exacerbation
- Number of airway clearance tasks completed.

This will assist with monitoring of intervention uptake and feasibility.

Other data to be collected from EPIC across the intervention and control groups include:

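### Staff who decline recording are not interviewed, whereas caregivers who decline are interviewed with notes; no reason is given, and staff interviews are the only measure of a primary objective

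*Protocol*

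**What the plan says.** Section 4 of the protocol describes the caregiver and staff interviews in two neighbouring subsections. Most of the procedure is the same in both: confidentiality is explained, audio is recorded on MS Teams, the camera may be off, and the interviewee may stop or revoke consent. They part on declined recording:

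- Caregivers: "If participants decline to be recorded, the interview will proceed with the PI taking notes of discussion".
- CF MDT staff: "If participants decline to be recorded, the interview will not proceed".

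The staff subsection also sets the target: "We will aim to perform interviews with as many members of the CF MDT as possible, aiming a minimum of 5 staff members". For caregivers the target is "We aim to conduct interviews with up to 15 parents".

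The synopsis lists as a primary objective "To assess the impact and acceptability of the remote system monitoring and automated treatment plans on CF multidisciplinary team (MDT) experience". The only measure it lists for that objective is "Semi structured interviews with staff investigating beliefs, acceptability and feasibility of the remote symptom monitoring and automated treatment plan care model". The objectives table in section 3 agrees, naming MDT interviews at 3 and 12 months as the sole data source.

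Section 6 (Qualitative analysis) plans inductive thematic analysis of transcripts in NVivo. Section 7 (Data storage) describes interview data as audio recordings that are transcribed and uploaded. Neither section says what happens to written notes.

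**The concern.** The same event has opposite consequences in the two groups, and nothing in the protocol explains why. The stricter rule falls on the group with less to spare. The staff target may be as low as 5, and no second instrument is listed for MDT experience, whereas the family objective also has overall service satisfaction. A staff member who is willing to be interviewed but not recorded contributes nothing to a primary outcome.

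Two things are at stake. The first is avoidable loss of data, which occurs whatever the reason for declining. The second is possible selection: if unwillingness to be recorded goes with a particular view of the new model, the range of views in the interviews would not reflect the range in the team. The setting makes this conceivable. The trial has a single site, and "Members of the CF MDT will be approached by the principal investigator via email"; the Recruitment text identifies that investigator as a physiotherapist in the same service. Section 5 notes that the CF team helped design the intervention and lists extra unfunded workload for the team as a known risk.

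**Working it through.** The protocol gives no figure for this point, so there is none to reproduce. The check compares the texts and adds a short illustration.

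**1. The rules side by side**

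| | Caregivers | CF MDT staff |
|---|---|---|
| Recording declined | Interview goes ahead with notes | No interview |
| Camera may be off | Yes | Yes |
| May stop or revoke consent | Yes | Yes |
| Target | Up to 15 | As many as possible, at least 5 |
| Other listed measure for the objective | Overall service satisfaction | None |
| Reason given for the rule | None | None |

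Destruction of audio after transcription (section 7) and de-identified quotation (section 6) apply to both groups. The shared safeguards therefore do not account for the difference.

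**2. What a declined recording costs**

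The contacts between team and family are counted separately under the feasibility objective. They measure workload, not experience or acceptability, so they are unaffected by the rule and cannot replace an interview. One person lost, as a share of the minimum target, is 1/5 = 20%. This is a share of the target and not of the team, whose size is not given. If many more than 5 staff are willing, the share is smaller; if nobody declines recording, the loss is nil.

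**3. Whether selection follows**

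Let c be the true share of staff critical of the model, dc the rate of declining recording among them, and dn the rate among other staff. The critical share among those interviewed is

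c(1 − dc) / [c(1 − dc) + (1 − c)(1 − dn)].

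All values below are assumptions; none is in the protocol. Take c = 40%.

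| dc | dn | Calculation | Critical share among interviewed |
|---|---|---|---|
| 10% | 10% | 0.36 / (0.36 + 0.54) | 40% (no selection) |
| 30% | 10% | 0.28 / (0.28 + 0.54) | 34% |
| 50% | 10% | 0.20 / (0.20 + 0.54) | 27% |
| 10% | 30% | 0.36 / (0.36 + 0.42) | 46% |

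Equal rates give no selection, and unequal rates can move the mix either way. The formula shows only how the mix of interviewees could change; the planned analysis reports themes and has no acceptability score or proportion.

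**4. Whether the caregiver rule can be carried over**

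The protocol already regards notes as usable for caregivers, so the method is available. The analysis and storage text does not yet provide for notes in either group, and that gap has to be closed as well.

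**The case against.** The strongest reply is that this is not a contradiction. The rules concern different people, sit in separate subsections with separate information sheets and interview guides, and each can be followed as written. Requiring a recording to obtain verbatim transcripts is a legitimate choice in qualitative research, and no planned analysis compares families with staff. The protocol also reduces reluctance: the camera may be off, audio is destroyed once transcribed, quotations are de-identified, and consent may be revoked. A wary staff member can refuse the invitation altogether, so the extra loss from the recording rule may be small or nil.

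Much of this stands. The two rules can operate together, and the protections are real. What remains is that both groups have the same protections, that only one has the notes option, and that the group without it is the one with the smaller minimum and no other measure. A need for verbatim text would apply to caregivers equally, and the protocol waives it for them.

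A reader might go further and infer that the rule removes the critics, so that MDT acceptability will look better than it is. The documents do not support that. Nothing says who would decline, how many would, or what their views would be, and staff may dislike being recorded for reasons unrelated to the model. With thematic analysis there is no estimate to be biased upward; the most that can be said is that a theme could be missed.

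**Conclusion.** The point holds as an unexplained difference in procedure that needlessly gives up data. For a primary objective with one listed measure and a minimum target of 5, the staff rule turns away anyone willing to be interviewed but not recorded, against the stated aim of reaching as many of the team as possible. Each such person equals 20% of the minimum target. That figure rests only on the target of 5 and does not predict how many will be lost.

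Selection is a possibility, conditional on declining being related to opinion. Neither its size nor its direction can be derived from the protocol. This is a minor improvement, worth making because it is easy.

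**What to change.** 1. In section 4, Semi structured interviews (CF MDT), replace the sentence on declined recording with the caregiver rule: the interview goes ahead and written notes are taken. Change the staff information and consent form to match.
2. In section 6 (Qualitative analysis) and section 7 (Data storage), state that written notes are stored and coded alongside transcripts, for caregivers and staff alike. Let the text on revoked consent in both interview subsections cover notes as well as recordings and transcripts.
3. Report how many staff were invited, how many declined interview, how many declined recording, and how many interviews in each group came from notes. A reader can then see whether the issue arose.

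The cost is a few sentences in the protocol, a change to the staff consent form, and less verbatim detail for interviews held from notes, a loss the plan already accepts for caregivers. If the investigators prefer to require recording for staff, the protocol should say why, and the reporting in item 3 is still needed.

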5 SAFETY MONITORING AND REPORTING

Adverse events (non-serious and serious) will be captured from the time of first administration of the intervention until conclusion of the intervention and all events will be followed until resolution or stabilisation.

Risks:

Risk/Benefit assessment

Known potential risks

- Increased burden of care to families by having to fill out the symptom surveys twice a week
 - o Survey will take approximately 3 minutes to fill out each time
- Participants not filling out the survey and therefore not gathering enough data to assess feasibility/effectiveness
- Increased workload for CF team without extra funding
 - o The pilot allows patients and families to directly contact the CF team which may increase contacts

Study Name: Acceptability, feasibility and impacts of remote symptom monitoring and automated treatment plans in children with Cystic Fibrosis (CF) on highly effective modulators: a pilot randomised controlled trial.

Protocol Number: 91117

Version & date: version 2, 28.10.2022

- The pilot may identify more pulmonary exacerbations compared to usual care which may increase contacts with CF team
- Underestimating/overestimating pulmonary exacerbations in patients leading to changes in treatment
 - Underestimating: the system may miss small exacerbations where families would normally self-initiate antibiotics and increase airway clearance, thereby undertreating
 - Overestimating: the system may over detect small exacerbations where families would normally not initiate antibiotics and increase physiotherapy, thereby leading to increased utilisation of antibiotics, however increased airway clearance may benefit the patient without clinical harm.

Known potential benefits

- It is well known that earlier detection and aggressive treatment of pulmonary exacerbations leads to better outcomes in people with CF
- Increased and clearer pathways of communication with CF team
- Continuous rather than episodic care
- Increased participant understanding of what an exacerbation entails
- Symptom monitoring storage in EPIC to help inform traditional CF clinic reviews and improving in-clinic efficiency
- Ongoing symptom monitoring helping to guide ongoing treatment decisions

Assessment of potential risks and benefits

- Underestimating/overestimating pulmonary exacerbations in patients leading to changes in treatment
 - Utilisation of a survey based on a validated survey
- Increased burden of care to families by having to fill out the symptom surveys twice a week
 - Patient choice to fill out survey
- Increased workload for CF team without extra funding
 - Mostly automated system, relieving large burden on CF team
 - CF team involved in design of the intervention

6 Analysis:

STATISTICAL METHODS

Methods of analysis

Quantitative analysis:

Statistical analysis will be performed utilizing Statistical Package for the Social Sciences (SPSS). Descriptive statistics will be presented as mean (standard deviation, SD) or median (interquartile range, IQR). Categorical variables will be reported descriptively using frequency (n) and proportion (%).

Primary analysis:

1. To assess the **uptake and feasibility** of the remote monitoring and automated treatment plans
 - a. Total number of symptom surveys completed will be compared to total number of surveys expected and presented as a percentage.
 - b. Total number of tasks completed will be compared to expected number of tasks completed and presented as a percentage.
 - c. Number of contacts between CF team and family will be collated and compared between the intervention and control group using paired t tests or the non-parametric equivalents.

Secondary:

1. To understand **changes in outcome measures** over time between the two groups in children on highly effective modulators
 - Number of exacerbations detected
 - Total number of exacerbations per year will be calculated in each arm and presented descriptively. Comparison between groups will occur using t-tests or Chi squared test (or non-parametric alternatives as required)
 - Change in FEV₁
 - Data will be expressed as litres and percentage predicted. For each individual the FEV₁ at study entry will be compared to the FEV₁ at study completion, to determine the change in FEV₁. The average change in FEV₁ between the intervention and control group will then be compared using t-tests or Chi squared test (or non-parametric alternatives as required).
 - Number of admissions
 - Total number of admissions per year will be calculated in each arm and presented descriptively. Comparison between groups will occur using t-tests or Chi squared test (or non-parametric alternatives as required)
 - Hospital length of stay
 - Total number of hospital days per year will be calculated in each arm and presented descriptively. Comparison between groups will occur using t-tests or Chi squared test (or non-parametric alternatives as required)
 - CFQ-R
 - Total score (mean and standard deviation) will be presented descriptively and comparison between groups will occur using t-tests or Chi squared test (or non-parametric alternatives as required)
 - EQ-5D-Y
 - Total score (mean and standard deviation) will be presented descriptively and comparison between groups will occur using t-tests or Chi squared test (or non-parametric alternatives as required)

2. To assess the **cost-effectiveness** of the remote monitoring and automated treatment plans compared to usual care by undertaking a health economic evaluation from both the perspective of the healthcare system and caregivers.
 - a. The cost of the new model will be estimated from the study protocol and budgets.
 - b. Difference in the patient's quality of life (EQ-5D-Y and CFQ-R) will be measured within the trial period for each arm and calculated using an area under the curve method.
 - c. Health service cost from hospital linked data along with patient costs will also be incorporated
 - d. Cost-effectiveness estimates of a cost per exacerbation avoided and cost per QALY for the new model compared with standard care will be generated for the trial period to justify the value of the new model of health monitoring.
 - e. Sensitivity analyses will be used to explore the variation in data. Wide cost confidence intervals are expected with a pilot study. The data collection will however inform acceptability and feasibility of economic data and contribute to the case or otherwise for a full trial.

Qualitative analysis:

Primary analysis:

1. To assess the **impact and acceptability** of the remote system monitoring and automated treatment plans on **family experience** (measured as experience of the program; acceptability of the program) compared to usual care;
2. To assess the **impact and acceptability** of the remote system monitoring and automated treatment plans on **CF MDT experience** (measured as experience of the program; acceptability of the program) compared to usual care.

Semi structured interview transcripts will be imported into NVivo for analysis. Inductive thematic analysis will be used, where initially text will be coded relating to factors influencing family and CF MDT perceptions and attitudes to the new model of care. Themes will be developed relating to codes, emerging inductively from the data. An audit trail will be produced to keep a record of coding decisions. De-identified quotations will be used from the transcripts to illustrate important aspects of parent's and the MDT staff attitudes to the new model of care versus usual care.

